6.2 Supportive Care Guidelines-Crisis Protocol

Anxiety is measured by the GAD-7 at baseline and weeks 7 and 13. Depression is measured by the PHQ-9 at baseline and at weeks 7 and 13. When the data from either of these two forms are filled out, the study staff will document the scores to ensure participants have not indicated a significant worsening in anxiety or depression scores (1 standard deviation increase [rounded to the nearest integer] on the GAD-7 (Change \geq 4)⁷⁵ or PHQ-9 (Change \geq 6)⁷³ from baseline]. If there has been a significant change, the Project Manager will initiate the Crisis Protocol and complete a Crisis Protocol Event Form. During the course of a regularly scheduled participant contact, it may become evident that there is a need for immediate evaluation (e.g., active suicidal ideation, active psychotic symptoms, disorientation). Staff will be instructed to follow the Crisis Protocol and complete the Crisis Protocol Event Form. In both cases, the participant may be referred for mental health care by their primary care physician or by an emergency department physician.

Study staff will follow the steps outlined in the Crisis Protocol and participants will receive information about safety precautions and procedures to follow in the event of a crisis (i.e., the participant becomes imminently suicidal). Because active suicidal ideation is an exclusion criterion for the study, we anticipate that the risk of participants becoming suicidal during the study will be minimal. Further, in our prior studies, no participants randomized into the study became imminently suicidal. All study staff (therapists, research staff) will receive training on the Crisis Protocol and coping with participant distress that may be experienced during the consent, assessment and treatment procedures. In addition, there will be regular study team meetings to discuss clinical issues. [name] will review the status and progress of participants with the study therapists on a regular (at least monthly) basis. All participants will be contacted at Week 7 and Week 13 to assess the primary outcomes and depressive

Cultural and Linguistic Adaptation of a Telephone-Based Intervention to Treat Depression and Anxiety in Hispanic Cancer Survivors

Wake Forest Baptist Comprehensive Cancer Center
WFBCCC # 01220

symptoms. Additionally, study therapists will attempt to reach participants who miss a session by calling the participant twice in a one-week period. If the therapist is unable to contact the participant by phone, the therapist will send the participant a letter with a request that the participant contact the therapist regarding interest in continuing the study sessions.

6.3 Duration of the Intervention

CBT Intervention. CBT will consist of 12 individual weekly psychotherapy sessions with a study therapist by telephone and an accompanying workbook. We have used this treatment in 4 previous RCTs. The 12-chapter workbook focuses on techniques that have demonstrated efficacy in treating adults with an anxiety disorder and is currently being used in an ongoing for rural post-treatment cancer survivors.^{45,4647-51}

All participants receive 12 identical chapters according to their language preference. To tailor the intervention to anxiety and depressive symptoms, participants are instructed to choose 2 chapters from a menu of 5 chapters (e.g. pain, more focused information on changing behavior related to anxiety or depression, etc.). Workbook chapters target issues specific to cancer survivors, such as (a) fear of recurrence (most commonly reported source of distress in survivors across different types of cancer);^{8,9,13,24,38-48} (b) lasting effects of treatment on health, ongoing symptoms of fatigue and physiologic effects of cancer treatment;^{38,39,42,44,48-50} (c) late effects of cancer treatment (the possibility of developing other diseases);^{14,38,45} (d) concerns about reproductive ability and higher risk of cancer for their children;^{50,51} and (e) distress related to changes in body image and sexuality.^{14,41,45}

There will be weekly telephone sessions with the study therapist that will last 45 to 50 minutes. The participant and therapist will review the assigned chapter and assignments during weekly telephone sessions. In order to ensure privacy, every participant will be asked if he/she needs to reschedule the appointment due to a lack of privacy.

Coach training and supervision. Study coaches will be bilingual licensed mental health providers who have the ability to conduct therapy in both English and Spanish. Training will include use of the treatment manual, didactic presentations, readings, and role plays. The competency of coaches in delivering CBT-T will be evaluated with a measure developed and used by [name].^{47,48} Coaches who fail to demonstrate competency (mean competency score < 6 on a scale of 1 to 8) will receive additional training and exposure to role play exercises until competency is demonstrated. Also, coaches must achieve ≥80% adherence across the sessions before contacting any potential participants. If any coach fails to achieve this level, the PI will determine if there are specific components across sessions that are routinely omitted or implemented incorrectly and will retrain the coach in the identified treatment components. The PI will meet with the coaches weekly to discuss cases, review adherence and competence ratings, and answer any questions regarding the administration of the protocol. Any areas of non-adherence will be reviewed with the coaches.

Cultural and Linguistic Adaptation of a Telephone-Based Intervention to Treat Depression and Anxiety in Hispanic Cancer Survivors

Wake Forest Baptist Comprehensive Cancer Center
WFBCCC # 01220

6.4 Duration of Follow Up

Participants will be involved in a 12-week intervention and will complete the follow-up assessment immediately upon completion of the intervention.

6.5 Criteria for Removal from Study

Participants will be removed from study for the following reasons: the protocol intervention and any protocol-required follow-up period is completed, serious adverse event, lost to follow-up, withdraw consent, PI removes from study, or death. Participants also have the option to discontinue the intervention but continue in the study for follow-up purposes. For subjects who are enrolled, site staff must contact the subject at the next study visit with at least 5 attempts. After 5 documented contact attempts the subject will be considered lost to follow-up. Site staff must complete a Participant Status Change Form in RedCap.

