7.0 Adverse Events List and Reporting Requirements

REPORTING ADVERSE AND SERIOUS ADVERSE EVENTS

Reportable Adverse Events

An adverse event (AE) is defined as any untoward or unfavorable medical occurrence in a human subject, including any clinically significant abnormal sign (for example, abnormal physical exam or laboratory finding), symptom, or disease, temporally associated with the subject's participation in the research, whether or not considered related to the subject's participation in the research. The burden of collecting and reporting data on every possible AE is excessive and therefore, study staff will report all serious adverse events (SAEs) and selected described below.

SAEs and AEs will be ascertained by study staff for all participants at Weeks 7 and 13. Study staff will administer the Adverse Event Ascertainment Form to specifically query participants about safety events at weeks 7 and 13. In addition, adverse events may also be reported to study staff spontaneously through telephone calls, emails or other correspondence. In addition to local reporting requirements, all SAEs and selected AEs will be recorded on the Adverse Event Form by clinic staff.

AEs will be assessed according to the grade associated with the CTCAE term. AEs that do not have a corresponding CTCAE term will be assessed according to the general guidelines for grading used in the CTCAE v5.0.. A copy of the CTCAE can be found at http://ctep.cancer.gov/protocolDevelopment/electronic_applications/ctc.htm

Serious Adverse Events

Definition: Regulations at 21 CFR §312.32 (revised April 1, 2014) define an SAE as any untoward medical occurrence that at any dose or intervention level has one or more of the following outcomes: A Serious Adverse Event (SAEs) is defined if it results in ANY of the following outcomes:

- Death
- Life-threatening
- Results in inpatient hospitalization or prolongation of existing hospitalization for \geq 24hours
- A persistent or significant incapacity or substantial disruption of the ability to conduct normal life functions
- A congenital anomaly/birth defect

Cultural and Linguistic Adaptation of a Telephone-Based Intervention to Treat Depression and Anxiety in Hispanic Cancer Survivors

Wake Forest Baptist Comprehensive Cancer Center
WFBCCC # 01220

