- Important Medical Event (IME) that may not result in death, be life threatening, or require hospitalization may be considered serious when, based upon medical judgment, they may jeopardize the patient or subject and may require medical or surgical intervention to prevent one of the outcomes listed in this definition. (FDA, 21 CFR 312.32; ICH E2A and ICH E6).

Reporting Requirements for above Study Descriptions:

- All unexpected hospitalizations regardless of grade
- All Grade 5 toxicities (deaths-expected and unexpected)
- All unexpected Grade 4 toxicities
- All additional reporting requirements as outlined in the protocol

Selected Adverse Events

A select list of adverse events include suicide attempts, psychosis, worsening anxiety, worsening depression, and suicidal ideation, should be reported as an adverse event, regardless of whether they resulted in an ER visit or hospitalization.

Definition of Worsening Anxiety or Depression

An adverse event form should be completed for any participant who indicates a significant worsening in anxiety or depression scores (1 standard deviation increase (rounded to the nearest integer) on the GAD-7 (Change ≥ 4)⁷⁵ or PHQ-9 (Change ≥ 6)^{73,74,51} from baseline). If there is a need for immediate treatment (e.g., active suicidal ideation, active psychotic symptoms, disorientation, and active substance abuse) at any point in time, staff persons will notify the co-PIs. In both cases, the participant may be referred for psychiatric care.

Data and Safety Monitoring: As adverse event reports are collected, all adverse events will be identified and reported to the co-principal investigators. The co-principal investigators are responsible for the review of all adverse event reports and determining whether any changes in the study protocol or informed consent are required to insure subject safety and welfare.

Clinical Monitoring: The co-PIs will meet with the study staff weekly to provide supervision and review the clinical status of all participants. Study staff will also notify at least one supervisor immediately if a patient shows the need for urgent treatment (e.g., suicidal intent, active psychosis). This type of information will be communicated immediately, with consultation about an appropriate course of action.

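### Section 6.5 takes participants off study for a serious adverse event without qualification, so read literally a recoverable event ends the remaining Week 7 and 13 checks and counts against retention

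*Combined protocol and SAP*

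**What the plan says.** Section 6.5 states in mandatory terms that participants come off study for a list of reasons. After completion of the intervention and follow-up, the list reads "serious adverse event, lost to follow-up, withdraw consent, PI removes from study, or death". Removal by the PI is a separate item, so investigator discretion does not govern the SAE item. The next sentence adds: "Participants also have the option to discontinue the intervention but continue in the study for follow-up purposes".

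Section 7.0 defines an adverse event as one that counts "whether or not considered related to the subject"'s participation. One route to seriousness is that the event "Results in inpatient hospitalization or prolongation of existing hospitalization for" at least 24 hours.

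On follow-up, section 6.2 says "All participants will be contacted at Week 7 and Week 13", and section 7.0 says "SAEs and AEs will be ascertained by study staff for all participants at Weeks 7 and 13". Between those contacts, "adverse events may also be reported to study staff spontaneously through telephone calls, emails or other correspondence". For urgent psychiatric need, section 7.0 (Clinical Monitoring) asks for immediate communication "with consultation about an appropriate course of action" and does not mention removal.

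Section 5.1.1 defines retention as the proportion of participants who complete the Week 13 visit, with no exception for SAE removals, and sets the adherence threshold at 9 of 12 sessions. Section 9.1 compares retention with 75% by a one-sample binomial test. The Table 3 footnote accepts assessments up to 6 weeks late.

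**The concern.** Stopping treatment and leaving the study are different events, and the second sentence of 6.5 shows that the team knows this. The SAE item nevertheless sits on the leaving side. A participant admitted for a day or two for something unrelated, and well again within a week, would come off study under the text as written.

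Two things are at stake.

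- **Safety information.** Scheduled questioning about adverse events happens only at Weeks 7 and 13. The PHQ-9 and GAD-7 worsening triggers for the Crisis Protocol and the adverse event form depend on the same visits. After removal, a new event would come to light only if someone reported it spontaneously. These people entered with a GAD-7 of at least 10 and/or a PHQ-9 of at least 8, and they have just had a serious event.
- **A primary outcome.** Retention is meant to show whether participants will stay. Someone willing and able to do the Week 13 call, but removed by rule, counts as a failure of retention.

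**Working it through.** **Inputs from the documents.** N = 12 (9.3, 9.4); retention = Week 13 completers / participants (5.1.1); reference value 75% (9.1); stated precision 28% (9.3); PHQ-9, GAD-7 and adverse event ascertainment at Weeks 7 and 13 (Table 3). No SAE rate is given, so the rates below are assumptions.

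**1. The plan's own precision figure.** The Wald half-width at a proportion of 0.5 is 1.96 × √(0.5 × 0.5 / 12) = 0.283. This reproduces the stated 28%, which is not in dispute.

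**2. Scheduled checks lost, by timing of removal.**

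| Removal | PHQ-9 lost | GAD-7 lost | Adverse event ascertainments lost |
|---|---|---|---|
| Before Week 7 | 2 | 2 | 2 |
| Between Weeks 7 and 13, or SAE first learned of at the Week 7 contact | 1 | 1 | 1 |
| SAE first learned of at the Week 13 contact | 0 | 0 | 0 |

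**3. Effect on retention.** One removed participant who would otherwise have finished costs 1/12 = 8.3 percentage points.

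**4. How often.** With an assumed SAE risk p per participant by Week 13, P(at least one in 12) = 1 − (1 − p)^12, and the expected drop in retention is at most 100p points.

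| Assumed p | P(at least one SAE in 12) | Expected drop, at most |
|---|---|---|
| 2% | 1 − 0.98^12 = 22% | 2 points |
| 5% | 1 − 0.95^12 = 46% | 5 points |
| 10% | 1 − 0.90^12 = 72% | 10 points |

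As measures of the rule's effect these are upper bounds: some SAEs would prevent the visit anyway, and some are first learned of at Week 13. If retention would otherwise be 75% and SAEs are independent of it, the expected drops are 0.75 × p = 1.5, 3.75 and 7.5 points.

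**5. Effect on the planned test against 75%.** Section 9.1 does not say whether the test is exact or approximate, so both are shown. The exact two-sided p-value sums the probabilities of all counts no more likely than the one observed under Binomial(12, 0.75). The score statistic is z = (x/12 − 0.75) / √(0.75 × 0.25 / 12), with denominator 0.125.

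| Retained | Exact p | z | Score p |
|---|---|---|---|
| 12/12 | 0.0317 + 0.0143 = 0.046 | 2.00 | 0.046 |
| 11/12 | 0.32 | 1.33 | 0.18 |
| 10/12 | 0.74 | 0.67 | 0.50 |
| 9/12 | 1.00 | 0.00 | 1.00 |
| 8/12 | 0.51 | −0.67 | 0.50 |
| 7/12 | 0.19 | −1.33 | 0.18 |
| 6/12 | 0.0544 + 0.0317 = 0.086 | −2.00 | 0.046 |
| 5/12 | 0.014 | −2.67 | 0.008 |

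At the two-sided 5% level, losing one participant changes the result at 12/12 to 11/12 under both tests. It also changes it at one lower step: 6/12 to 5/12 with the exact test, 7/12 to 6/12 with the score test. At every other step, including those below 5/12, the result is the same before and after.

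**The case against.** The best counter-argument is that 6.5 does not mean what it literally says. Its list includes completion and death, so it could be a catalogue of off-study reasons for the Participant Status Change Form. The option to stop sessions but stay for follow-up comes next, followed by a rule of at least 5 contact attempts for enrolled subjects. Sections 6.2 and 7.0 speak of all participants at Weeks 7 and 13, and urgent psychiatric events are handled by referral and consultation. All this suggests that stopping the intervention may have been the intent.

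That stands as evidence of intent, but it does not undo the rule. The follow-up option belongs to the participant, does not mention SAEs and is not worded as an exception. The phrase about all participants can mean those still on study, and a removed subject may no longer count as enrolled. Staff who follow the list would take the person off study.

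It is also fair that the effect is uncertain and probably small. The SAE rates are assumed, PHQ-9 and GAD-7 are only summarised descriptively (9.2), and no stated go/no-go rule depends on retention. This limits the weight of the point without removing it.

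A reader might infer that safety oversight ends with removal. The documents do not support that: Appendix C keeps qualifying events reportable to the DSMC for 30 days after the last study treatment and asks for updates on reported events. It is the scheduled checks that end.

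**Conclusion.** The point holds as a defect of wording with a real, modest consequence. Followed literally, 6.5 discards up to two rounds of scheduled safety and symptom checks for a participant with a recoverable SAE, and it lowers a primary outcome by 8.3 points for each participant who would otherwise have finished. How often this happens rests wholly on the assumed SAE rate. At 2% to 10%, the expected drop of at most 2 to 10 points is well inside the plan's 28% precision.

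Two stronger conclusions are tempting and should be resisted. One is that the rule will generally change the retention finding. It does so at only two steps under either form of the test, and the upper one needs otherwise perfect retention. The opposite claim, that it can never change the finding, is also wrong, because 12/12 to 11/12 loses the only result significantly above 75%. The other is that the team clearly intended automatic removal; the surrounding text leaves that open. The change is worth making because it costs almost nothing and protects both follow-up and the meaning of retention.

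**What to change.** In 6.5, take the SAE item off the list of reasons for leaving the study and make it a possible reason to pause or stop sessions, at investigator judgement. Add that Week 7 and 13 assessments continue unless the participant withdraws consent, is lost to follow-up, dies or is unable to take part. It would do no harm to confirm that all enrolled participants stay in the retention denominator, which 5.1.1 already implies.

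The cost is one or two sentences. No visits are added beyond those in Table 3, and the Participant Status Change Form already exists to record the change. The fix restores the scheduled safety checks and the retention count. It does not fully cure adherence: a participant whose sessions are stopped before the ninth would still miss the 9-of-12 threshold.

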7.0 Adverse Events List and Reporting Requirements

REPORTING ADVERSE AND SERIOUS ADVERSE EVENTS

Reportable Adverse Events

An adverse event (AE) is defined as any untoward or unfavorable medical occurrence in a human subject, including any clinically significant abnormal sign (for example, abnormal physical exam or laboratory finding), symptom, or disease, temporally associated with the subject's participation in the research, whether or not considered related to the subject's participation in the research. The burden of collecting and reporting data on every possible AE is excessive and therefore, study staff will report all serious adverse events (SAEs) and selected described below.

SAEs and AEs will be ascertained by study staff for all participants at Weeks 7 and 13. Study staff will administer the Adverse Event Ascertainment Form to specifically query participants about safety events at weeks 7 and 13. In addition, adverse events may also be reported to study staff spontaneously through telephone calls, emails or other correspondence. In addition to local reporting requirements, all SAEs and selected AEs will be recorded on the Adverse Event Form by clinic staff.

AEs will be assessed according to the grade associated with the CTCAE term. AEs that do not have a corresponding CTCAE term will be assessed according to the general guidelines for grading used in the CTCAE v5.0.. A copy of the CTCAE can be found at http://ctep.cancer.gov/protocolDevelopment/electronic_applications/ctc.htm

Serious Adverse Events

Definition: Regulations at 21 CFR §312.32 (revised April 1, 2014) define an SAE as any untoward medical occurrence that at any dose or intervention level has one or more of the following outcomes: A Serious Adverse Event (SAEs) is defined if it results in ANY of the following outcomes:

- Death
- Life-threatening
- Results in inpatient hospitalization or prolongation of existing hospitalization for \geq 24hours
- A persistent or significant incapacity or substantial disruption of the ability to conduct normal life functions
- A congenital anomaly/birth defect

Cultural and Linguistic Adaptation of a Telephone-Based Intervention to Treat Depression and Anxiety in Hispanic Cancer Survivors

Wake Forest Baptist Comprehensive Cancer Center
WFBCCC # 01220

- Important Medical Event (IME) that may not result in death, be life threatening, or require hospitalization may be considered serious when, based upon medical judgment, they may jeopardize the patient or subject and may require medical or surgical intervention to prevent one of the outcomes listed in this definition. (FDA, 21 CFR 312.32; ICH E2A and ICH E6).

Reporting Requirements for above Study Descriptions:

- All unexpected hospitalizations regardless of grade
- All Grade 5 toxicities (deaths-expected and unexpected)
- All unexpected Grade 4 toxicities
- All additional reporting requirements as outlined in the protocol

Selected Adverse Events

A select list of adverse events include suicide attempts, psychosis, worsening anxiety, worsening depression, and suicidal ideation, should be reported as an adverse event, regardless of whether they resulted in an ER visit or hospitalization.

Definition of Worsening Anxiety or Depression

An adverse event form should be completed for any participant who indicates a significant worsening in anxiety or depression scores (1 standard deviation increase (rounded to the nearest integer) on the GAD-7 (Change ≥ 4)⁷⁵ or PHQ-9 (Change ≥ 6)^{73,74,51} from baseline). If there is a need for immediate treatment (e.g., active suicidal ideation, active psychotic symptoms, disorientation, and active substance abuse) at any point in time, staff persons will notify the co-PIs. In both cases, the participant may be referred for psychiatric care.

Data and Safety Monitoring: As adverse event reports are collected, all adverse events will be identified and reported to the co-principal investigators. The co-principal investigators are responsible for the review of all adverse event reports and determining whether any changes in the study protocol or informed consent are required to insure subject safety and welfare.

Clinical Monitoring: The co-PIs will meet with the study staff weekly to provide supervision and review the clinical status of all participants. Study staff will also notify at least one supervisor immediately if a patient shows the need for urgent treatment (e.g., suicidal intent, active psychosis). This type of information will be communicated immediately, with consultation about an appropriate course of action.

The Data Safety Monitoring Committee (DSMC) is responsible for reviewing SAEs for WFBCCC Institutional studies as outlined in Appendix D. All Adverse Events that occur during protocol intervention and are coded as either 1) unexpected grade 4, 2) unplanned inpatient hospitalization ≥ 24 hours (regardless of grade), or grade 5 (death) must be reported to the DSMC using the SAE console in WISER.

All WFBCCC Clinical Protocol and Data Management (CPDM) staff members assisting a Principal Investigator in investigating, documenting and reporting an SAE qualifying for DSMC reporting are responsible for informing a clinical member of the DSMC as well as the entire committee via the email notification procedure of the occurrence of an SAE.

**Cultural and Linguistic Adaptation of a Telephone-Based Intervention to Treat Depression and Anxiety
in Hispanic Cancer Survivors**

Wake Forest Baptist Comprehensive Cancer Center
WFBCCC # 01220

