5.2 Secondary Outcomes

5.2.1 Anxiety – GAD-7

The **GAD-7**⁵³ is a self-report measure of DSM-IV symptoms of GAD. Participants rate 7 questions on a scale of 0 (not at all) to 3 (nearly every day); one additional question assesses the interference of these symptoms with functioning. The first 7 questions are summed to create a total score. It has been validated for use in the general population⁷⁰ and in primary care.⁵³ The GAD-7 has demonstrated good sensitivity (89%) and specificity (82%) in identifying GAD diagnoses when using a cut point of 10.⁵³ It also has good internal consistency (alphas = 0.89-0.92) and test-retest reliability (intraclass correlation = .83).^{53,70}

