5.2.2 Depressive Symptoms – PHQ-9

The **PHQ-9** is a self-report measure of DSM-IV symptoms of Major Depressive Disorder. Participants rate how often they have experienced nine symptoms over the past 2 weeks on a scale of 0 (not at all) to 3 (nearly every day). Responses are summed, with higher scores indicating greater depressive symptomatology. It has demonstrated good reliability and validity. The traditional cutoff for the PHQ-9 is a score ≥ 10 . However, ASCO guidelines recommend using a score ≥ 8 , based on a study of cancer outpatients⁷⁶ and a meta-analysis of use of the PHQ-9 for identifying depression in cancer patients.⁷⁷

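### On each scale separately, the score-change definition of worsening (GAD-7 +4, PHQ-9 +6) cannot be met by a participant who enters near that scale's maximum

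*Combined protocol and SAP*

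**What the plan says.** **Scales.** Section 5.2.1 on the GAD-7: "Participants rate 7 questions on a scale of 0 (not at all) to 3 (nearly every day"), and "The first 7 questions are summed to create a total score". Section 5.2.2 on the PHQ-9: respondents rate "nine symptoms over the past 2 weeks on a scale of 0 (not at all) to 3 (nearly every day"), and "Responses are summed, with higher scores indicating greater depressive symptomatology".

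**Definition of worsening.** Section 7.0 requires an adverse event form after a "1 standard deviation increase (rounded to the nearest integer) on the GAD-7 (Change ≥ 4") "or PHQ-9 (Change ≥ 6") from baseline. Worsening anxiety and worsening depression are listed there as two separate selected adverse events. The score change is the only definition given for either.

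**Second use of the rule.** Section 6.2 applies the same two thresholds, also joined by 'or', to the Week 7 and Week 13 scores: "If there has been a significant change, the Project Manager will initiate the Crisis Protocol and complete a Crisis Protocol Event Form".

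**Entry.** Section 3.1 sets lower score limits only (GAD-7 of 10 or more and/or PHQ-9 of 8 or more). Section 3.2 has no score-based exclusion, and section 3.0 says that people with severe symptoms are meant to enrol.

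Neither 6.2 nor 7.0 says what happens when the baseline score is too close to the scale maximum for the required rise.

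**The concern.** A fixed rise on a bounded scale needs room above the baseline score. The trial recruits people because their scores are high and sets no cap, so some participants may have too little room.

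Take a participant who enters with a GAD-7 of 19 and later scores 21, the worst possible value. The rise is 2, so by definition this is not worsening anxiety, and no other result on that scale could have been.

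Two things are at stake. First, the purpose of the score check in 6.2 is to make sure that participants have not significantly worsened. On a scale already near its top, the check returns a negative answer whatever happens. Second, a count of zero for worsening anxiety or worsening depression would mix participants who did not worsen with participants who could not be recorded as worsening. With 12 participants, even one of the latter affects how the safety listing reads.

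**Working it through.** **Inputs.** GAD-7: 7 items scored 0-3 (5.2.1). PHQ-9: 9 items scored 0-3 (5.2.2). Required rises: 4 and 6 (6.2, 7.0). Entry: GAD-7 ≥ 10 and/or PHQ-9 ≥ 8 (3.1). N = 12 (9.3).

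**The plan's own figures.** The thresholds are described as one standard deviation, rounded. The documents give no standard deviation, so 4 and 6 cannot be reproduced. Rounding implies values of about 3.5-4.5 and 5.5-6.5. The thresholds are taken as given below.

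**Step 1: highest baseline that can still reach the threshold** (maximum minus required rise).

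| | Maximum | Required rise | Highest workable baseline | Blocked baselines |
|---|---|---|---|---|
| GAD-7 | 7 × 3 = 21 | 4 | 21 − 4 = 17 | 18-21 |
| PHQ-9 | 9 × 3 = 27 | 6 | 27 − 6 = 21 | 22-27 |

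Of the scores that qualify for entry on each scale, the blocked ones are 4 of 12 GAD-7 values (10-21) and 6 of 20 PHQ-9 values (8-27).

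**Step 2: effect of the 'or'.** Count the possible score pairs.

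- All pairs: 22 × 28 = 616.
- Ineligible pairs (GAD-7 0-9 and PHQ-9 0-7): 10 × 8 = 80.
- Eligible pairs: 616 − 80 = 536.
- GAD-7 criterion blocked: 4 × 28 = 112.
- PHQ-9 criterion blocked: 6 × 22 = 132.
- Both blocked: 4 × 6 = 24.
- At least one blocked: 112 + 132 − 24 = 220.

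So 24 of 536 pairs can meet neither criterion, and 220 of 536 cannot meet at least one. These are counts of possible scores. They are not expected shares of participants.

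**Step 3: how likely it is to arise among 12.** The share of entrants in a blocked range is not in the documents, so it is an assumption, s. Expected number = 12 × s. Chance of at least one = 1 − (1 − s)^12.

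| Assumed s | Expected number | Chance of at least one |
|---|---|---|
| 2% | 0.24 | 22% |
| 5% | 0.6 | 46% |
| 10% | 1.2 | 72% |
| 20% | 2.4 | 93% |

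This is the chance that someone enters in a blocked range. For a worsening to be missed, that person must also deteriorate, not trigger through the other scale, and not be picked up by another route.

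**The case against.** The case on the other side has four parts.

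1. **The 'or'.** A reader might infer that the most distressed participants fall outside the score trigger altogether. The documents do not support that. A participant at the ceiling on one scale can still start the Crisis Protocol and an adverse event form through the other scale. Only the combination of GAD-7 ≥ 18 and PHQ-9 ≥ 22 closes both. This stands and limits the point to one scale at a time. It does not remove the point, because a rise on the PHQ-9 does not record worsening anxiety, and 7.0 lists the two events separately.

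2. **Other safeguards.** A reader might also infer that these participants go unmonitored. They do not. Sections 6.2 and 7.0 provide routes for urgent need that do not depend on score change. Suicidal ideation, psychotic symptoms and disorientation are given there only as examples. Section 7.0 adds ascertainment of adverse events at Weeks 7 and 13, spontaneous reports, and weekly review of clinical status by the co-principal investigators. Participants also speak weekly with a licensed therapist, and staff document every score. This stands too. These routes rest on judgement or on other events, however, and they do not supply the missing score rule.

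3. **No planned analysis depends on it.** Section 9 plans no adverse event rate or comparison, so it would be too strong to say that a planned estimate is biased. What remains is how the safety listing is read.

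4. **No stated number is wrong.** Every fixed change threshold on a bounded scale has a ceiling, and 5.2 does not contradict 6.2 or 7.0 figure against figure. That is correct. The defect is that the definition is silent over part of the score range that 3.1 admits.

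**Conclusion.** The concern holds scale by scale. By the protocol's own scoring, baseline GAD-7 18-21 cannot register worsening anxiety and baseline PHQ-9 22-27 cannot register worsening depression. The combined trigger is unreachable only when both scores are in those ranges. This part is exact and needs no outside figure.

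The number of participants affected is unknown. The table of assumed shares shows only that, unless such scores are rare, at least one such participant among 12 is quite possible.

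The consequence is modest: a gap in one trigger, and a listing in which a zero can mislead. It is still worth correcting, because the definition serves as a safety check and the correction is nearly free.

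**What to change.** **Protocol.** The investigators should reconcile the change thresholds in 6.2 and 7.0 with the 0-21 and 0-27 limits that follow from 5.2 and with the open-ended entry criterion in 3.1. How they do so is a clinical decision, and no threshold is proposed here. The same edit should state which score counts as baseline. Section 6.2 says both scales are measured at baseline, whereas Table 3 shows them at screening only and 6.1 repeats them only if more than 30 days have passed.

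**Safety listing.** Flag, per scale, participants with baseline GAD-7 of 18 or more (for worsening anxiety) and baseline PHQ-9 of 22 or more (for worsening depression). Report each worsening count with the number who could reach the threshold and the number who could not.

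**Cost.** A wording change and one extra flag per scale, computed from scores already collected. The downside is smaller denominators in an already small sample, so the counts should be shown as they are, without inference.
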